### HYPOTHESES:

1. Women who receive DMPA 4-6 weeks after delivery will be more likely than women who receive DMPA prior to hospital discharge to exclusively breastfeed for 6 months.
2. Women who receive DMPA 4-6 weeks after delivery will be as likely as women who receive DMPA prior to hospital discharge to use highly effective contraception (i.e. DMPA, intrauterine device (IUD), implant, sterilization, or lactational amenorrhea) at 6 months after delivery.
3. Women who receive DMPA 4-6 weeks after delivery will be no more likely than women who receive DMPA prior to hospital discharge to develop postpartum depression as measured by the Edinburgh Postnatal Depression Scale.(5)

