## 2. PREVIOUS RESEARCH

Postpartum contraception is important because unintended pregnancy rates range from 10%-20% in the first year postpartum.(6, 7) Lactational amenorrhea (LAM) can be effective contraception for up to 6 months.(8) However, many US women stop breastfeeding soon after delivery. By two weeks postpartum, an estimated 59% of US women started supplementation (2) and 37% of women stopped breastfeeding.(9) If sexually active and not using contraception, such women are at risk for unintended pregnancy.

Postpartum visits in the US generally occur 4-6 weeks after delivery.(10) Although 85% of women return for postpartum visits,(11) approximately half of women initiate sexual activity before six weeks postpartum and 82% are sexually active by 12 weeks postpartum.(12) Since ovulation can occur by 4 weeks postpartum in non-breastfeeding women,(13) experts recommend that women who are not exclusively breastfeeding should initiate contraception by 3 weeks postpartum.(14) Some also recommend that the postpartum visit should occur by 2-4 weeks postpartum in order to address contraception, breastfeeding, and postpartum depression,(14, 15) since postpartum depression affects 10%-15% of mothers (16) and can be associated with poor maternal-infant interactions and attachment.(17) Studies of the association of depression and breastfeeding discontinuation are conflicting.(18-20) One study of norethisterone enanthate given within 48 hours of delivery found an increased risk of postpartum depression,(21) but no studies have examined the effect of timing of DMPA administration on postpartum depression, contraceptive use, or breastfeeding.

Breastfeeding has many benefits, including immunologic protection and nutrition for the infant, more rapid uterine involution, decreased postpartum bleeding, and improved infant-bonding.(22) Exclusive breastfeeding for at least six months is recommended by the American College of Obstetricians and Gynecologists and the World Health Organization.(22, 23) However, only 41% of children in the National Immunization Survey were breastfed for 6 months.(24)

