- 1.) Group 1: An investigator will order DMPA to be administered prior to hospital discharge. The subject's subsequent DMPA injection will be due 11-13 weeks after the injection. The subject will follow up with her primary obstetrician or midwife for further DMPA administrations.
- 2.) Group 2: The subject will be asked to follow up with her primary obstetrician or midwife at 4-6 weeks after delivery for DMPA administration or to start a more effective form of contraception such as an IUD or implant, or to be scheduled for sterilization. She will be instructed to use condoms until her follow-up visit if she is not abstinent. She will also be instructed on emergency contraception use.

A questionnaire about breastfeeding intentions and whether lactogenesis II has occurred (i.e. the mother's "milk has come in") will be administered prior to discharge. Information about the delivery and postpartum course will be collected, including type of delivery, birth weight, gestational age, Apgar scores, and subject's height and weight at time of delivery. The subject's primary obstetrician or midwife will be notified of plans for administering the woman's next dose of DMPA. Routine postpartum care (including referrals for lactation consultation or behavioral health services) will be provided by the subject's primary obstetrician or midwife. Any subject who decides to use an alternate form of contraception after randomization will be followed per protocol. The 2-week follow-up phone contact will be scheduled prior to discharge.

**5.7 Follow-up contacts:** Subjects will be contacted by phone at the following time points:

1) Week 2: day 12-19 (goal day 14)	6) Week 16: day 108-118 (goal day 112)
2) Week 4: day 26-33 (goal day 28)	7) Week 20: day 136-146 (goal day 140)
3) Week 6: day 40-47 (goal day 42)	8) Week 24: day 164-174 (goal day 168)
4) Week 8: day 54-61 (goal day 56)	9) Week 28: day 192-202 (goal day 196)
5) Week 12: day 80-90 (goal day 84)	

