#### *OUTCOME ASSESSMENTS*

- A questionnaire about breastfeeding (including psychosocial factors related to breastfeeding and introduction of alternatives to breastmilk) and contraceptive use will be administered at each contact. Timing of lactogenesis II will be assessed at Week 2 unless it occurred prior to discharge. Timing of postpartum sexual activity initiation will also be assessed. At any point when the subject reports cessation of breastfeeding, a questionnaire will be administered to assess reasons for discontinuation.

- The Edinburgh Postnatal Depression Scale (EPDS) will be administered at each contact as a screening tool for postpartum depression.(5) If a subject scores  $\geq 12$  on the EDPS, she will be referred to the Magee Behavioral Health clinic or to a behavioral health clinic of her choice and her primary obstetrician or midwife will be notified.
- Subjects will be asked if they had any visits with their primary obstetrician, midwife, or any other provider since the last contact. Records will be requested from all reported visits.
- The next telephone contact will be scheduled (when applicable).

**5.8 Data analysis:** Analysis will be performed using Stata 10 (StataCorp LP, College Station, TX).

- 1) The primary analyses will use intention-to-treat data. The intention-to-treat group will be defined as all randomized subjects. Infants who are fed pumped breastmilk will be considered as breastfeeding. Exclusive breastfeeding will be defined as breastfeeding without introduction of alternatives to breastmilk. A secondary analysis looking only at women who received at least one injection of DMPA will also be performed.
- 2) Survival analysis will be used for all time series data, including time to discontinuation of breastfeeding and time to introduction of alternatives to breastmilk. Data will be censored at the last date of contact. Breastfeeding will be the outcome variable. The log-rank test will be used for unadjusted comparison of the groups and presented graphically using a Kaplan-Meier curve. Cox proportional hazards model will be used to control for age, race, education, marital status, and prior breastfeeding experience while examining the association between timing of DMPA administration and discontinuation of breastfeeding.

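### The log-rank test on time to first breastmilk alternative runs past the 6-month horizon of Hypothesis 1, so introductions after 6 months count as events

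*Combined protocol and SAP*

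**What the plan says.** Hypothesis 1 (section 1) is that women given DMPA at 4-6 weeks will be more likely "to exclusively breastfeed for 6 months". Section 2 gives the clinical background: "Exclusive breastfeeding for at least six months is recommended".

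Section 5.8, item 1, gives the definition: "Exclusive breastfeeding will be defined as breastfeeding without introduction of alternatives to breastmilk". It sets no age limit and does not say which alternatives count. Item 2 applies survival analysis to "time to introduction of alternatives to breastmilk" as well as to stopping breastfeeding, with a log-rank test and a Kaplan-Meier curve. The censoring rule is "Data will be censored at the last date of contact". The Cox model in the same item is written for discontinuation of breastfeeding only.

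The last two contacts in section 5.7 are "Week 24: day 164-174 (goal day 168") and "Week 28: day 192-202 (goal day 196"). The outcome assessments under 5.7 ask about feeding every time: a questionnaire covering "introduction of alternatives to breastmilk) and contraceptive use will be administered at each contact". No cut at 6 months is stated anywhere for the exclusivity endpoint.

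**The concern.** The hypothesis and the test have different horizons. The log-rank test compares hazards over all follow-up, so it uses events in the 10 to 20 days between month 6 and the week 28 call. Those events do not bear on whether a woman was exclusive for 6 months. How many enter depends partly on where in the 10-day call window she is reached.

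If women who reach 6 months then introduce alternatives for reasons unrelated to DMPA timing, the test gains events that carry no treatment signal, and the comparison moves toward no difference. The trial was prompted by concern that early DMPA harms breastfeeding, so that direction would be falsely reassuring.

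**Working it through.** **1. The plan's own figure.** Section 5.9 states 70 per group for 0.35 versus 0.60, two-sided Fisher's exact test, alpha 0.05, 80% power. Exact enumeration gives 80.95% at 70 per group and 79.9% at 69. Inflation: 140 / (0.90 × 0.85) = 183.0 (183.007), which rounds up to the stated 184. The figure reproduces. It concerns the 6-month proportion continuing any breastfeeding. No figure is stated for time to first alternative.

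**2. The window.** With 6 months taken as day 182, the week 28 call adds 192 − 182 = 10 to 202 − 182 = 20 days, and 196 − 182 = 14 at the goal day.

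**3. Women who can contribute a late event.** Randomized: 184 × 0.90 = 165.6, about 83 per arm. With 15% lost, the number still exclusive and followed at day 182 is 83 × (p₁ + p₂) × 0.85:
- 0.60 and 0.35: 83 × 0.95 × 0.85 = 67
- 0.45 and 0.25: 83 × 0.70 × 0.85 = 49
- 0.30 and 0.15: 83 × 0.45 × 0.85 = 32
- 0.15 and 0.05: 83 × 0.20 × 0.85 = 14

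All these exclusivity rates are assumptions. The first pair is section 5.9's pair for any breastfeeding. Exclusive breastfeeding cannot be more common than any breastfeeding, so 67 is a ceiling.

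**4. Power of the log-rank test by simulation.** Inputs: 83 per arm, 15% loss, two-sided 0.05, constant hazards to day 182 set by the 6-month proportions. After day 182 the hazard is the same in both arms, such that 30%, 60% or 80% of women still exclusive introduce alternatives within 20 days. Each data set is tested censored at day 182 and again followed to day 196. Monte Carlo error is about 1 point.

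| Exclusive at 6 months (group 2 vs group 1) | Power, cut at day 182 | Power, to day 196 (30/60/80%) | Points lost |
|---|---|---|---|
| 0.60 vs 0.35 (ceiling) | 0.90 | 0.84 / 0.79 / 0.75 | 6 / 11 / 15 |
| 0.45 vs 0.25 | 0.79 | 0.76 / 0.71 / 0.68 | 3 / 8 / 11 |
| 0.30 vs 0.15 | 0.71 | 0.69 / 0.67 / 0.65 | 2 / 4 / 6 |

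At 0.15 vs 0.05 the loss is about 1–3 points.

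**5. Separate check.** This used 70 per group, no loss, a cut at day 183, and a stated fraction introducing alternatives by day 196. At 0.60 vs 0.35 with an equal late hazard, power goes from 88% to 74% for a fraction of 0.50, and from 87% to 69% for 0.75. These losses exceed those in the table because the fraction is reached by day 196, not over 20 days. At 0.40 vs 0.15 the loss is at most about 4 points, and at 0.20 vs 0.05 it is 0 to 2.

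**6. When the assumption fails.** If the earlier hazard ratio continues after 6 months (same check, 0.60 vs 0.35, fraction 0.50), following to day 196 raises power from 86% to 97%.

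**7. Type I error.** Under no difference, rejection is 4.6% with either cut.

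**The case against.** The strongest reply is that section 5.1 promises the duration of exclusive breastfeeding, with no cap at 6 months, so full follow-up serves a stated aim. In addition, section 5.9 powers a 6-month proportion, and 5.8 item 3 provides chi-square or Fisher tests for proportions, so the 6-month question can be answered without the log-rank test. Both points are fair and keep this minor. They do not remove the mismatch, because the test named for the exclusivity endpoint still covers a period that Hypothesis 1 does not.

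Some stronger readings are tempting, and the documents do not support them.

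- *About 67 of 166 randomized women would be at risk at the plan's own rates.* The 0.60 and 0.35 are for any breastfeeding. Section 2 cites an estimated 59% of US women supplementing by two weeks, which points lower, although this trial recruits women who intend to breastfeed.
- *The late events come from the feeding recommendation, so dilution is certain.* The recommendation cited is a minimum of six months and does not say when alternatives start. An equal late hazard is an assumption, and step 6 shows the effect reversing without it.
- *The Cox hazard ratio is pulled toward 1.* The only Cox model specified is for discontinuation of breastfeeding, not for this endpoint.
- *The late events are solid foods.* Section 5.8 does not say whether solids count. Its definition does not exclude them.

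**Conclusion.** The mismatch is in the text: Hypothesis 1 ends at 6 months, while the log-rank test on time to first alternative runs to day 192-202. Whether it costs power depends on three quantities that the documents do not give: how many women are still exclusive at 6 months, how many of them introduce alternatives before the last call, and whether that late hazard is the same in both arms. With an equal late hazard and 30–80% introducing within 20 days, the loss is about 1–6 points at 0.30 vs 0.15 or lower and about 6–15 points at the ceiling. If the earlier hazard ratio persists there is a gain, but from a period outside the hypothesis.

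The point is confined to this one test. The 6-month proportion, type I error, sample size and the Cox model for discontinuation do not change. Nor does the Kaplan-Meier estimate at 6 months, provided introductions are dated. Severity: minor.

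**What to change.** In section 5.8, item 2, state that for Hypothesis 1 time to first alternative is administratively censored at a named 6-month day, for example day 182, using the reported date of first introduction. Say which alternatives count. Total breastfeeding duration keeps all follow-up, and exclusive duration over full follow-up can be reported as a secondary result.

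Keep the week 28 call. No contact falls between day 174 and day 192, so that call is what establishes status and dates up to the cut. The date of first introduction must be recorded, and the plan does not say that it is. If events were dated to the call instead, a woman who introduced alternatives between her week 24 call and day 182 would be censored as still exclusive. That gap is 182 − 174 = 8 to 182 − 164 = 18 days.

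The cost is a short addition to 5.8 and one dated item on the questionnaire. No extra contact or change in sample size is needed. The downside is that about two weeks of follow-up on exclusive duration leave the main test.

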##### **5.2 Criteria for selection of subjects**

Inclusion criteria:

- 1.) Age  $\geq$  18 years old at time of enrollment
- 2.) Gestational age of 24 0/7 weeks or higher, or postpartum, and have not already received DMPA
- 3.) Planning to deliver at Magee-Womens Hospital and to breastfeed
- 4.) Plans to use DMPA for postpartum contraception for at least 6 months, or plans to use DMPA for postpartum contraception until starting a more effective form of contraception such as an intrauterine device, contraceptive implant, or sterilization
- 5.) Willing and able to provide informed consent in English and to comply with study protocol

Exclusion criteria:

- 1.) Intolerance of irregular vaginal bleeding
- 2.) Severe coagulation disorder
- 3.) Severe liver disease (LFTs  $>2x$  upper limits of normal at time of randomization)
- 4.) Contraindications to breastfeeding: maternal HIV infection; active herpes simplex with breast lesions; active varicella; active, untreated tuberculosis; antineoplastic, thyrotoxic, or immunosuppressive medications; concern that the infant may have galactosemia
- 5.) History of breast cancer, reduction or augmentation surgery
- 6.) History of severe clinical depression
- 7.) Multiple gestation

**5.3 Subject recruitment:** Potential subjects will be identified during prenatal care by their primary obstetrician, midwife after receiving routine counseling for postpartum contraception, or on the

postpartum floor. If a woman is interested in the study, the primary obstetrician, postpartum nurse, or midwife will call the Center for Family Planning Research (CFPR). The potential subject will be scheduled for a visit in CFPR for screening and enrollment, or seen in-person on the postpartum unit.. Each subject will receive routine care from her primary obstetrician or midwife throughout her pregnancy, during delivery, and postpartum except as discussed per the research design.

**5.4 Screening and enrollment:** Pregnant women will be screened to ensure they meet all entry criteria.

Data collection on enrollment will include:

- a. Demographic information
- b. Medical history (including height and prepregnancy weight), obstetric and gynecologic history (including breastfeeding experience and contraceptive history)
- c. Psychiatric history (including depression, anxiety and substance use)
- d. Breastfeeding intentions as measured by the Infant Feeding Intentions Scale (29)

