- e. Psychosocial factors that can affect breastfeeding discontinuation, such as family/friend support for breastfeeding, plans for return to work/school, and confidence in ability to breastfeed (18)

**5.5 Subject allocation:** An independent individual will prepare allocation packets using a computer generated random number table. These packets will be placed in a sequentially numbered opaque tamper-resistant sealed envelope. Equal numbers of subjects will be randomly allocated to the following groups:

- 1.) Group 1. DMPA administration prior to hospital discharge.
- 2.) Group 2. DMPA administration at 4-6 weeks after delivery.

**5.6 Admission for delivery:** Research staff will check the hospital census daily for any study subjects. Obstetricians and midwives will be asked to contact the investigators after a subject's delivery and prior to hospital discharge. For women who will enroll in the study postpartum, a member of the postpartum staff or the medical team taking care of the patient will notify the patient of the available study. If the patient is interested in discussing the study with a member of the study team, the postpartum staff member will contact the research office. The verbal permission will be documented by the referring staff member, and filed in the research chart. A member of the research team will proceed with obtaining informed consent, and complete the visit on the postpartum unit. Day of delivery will be considered Day 0. Prior to hospital discharge (and ideally on postpartum day 1), subjects will be interviewed by research staff to assess whether she has initiated breastfeeding and remains eligible for the study. If she has not attempted breastfeeding at least once, does not plan to breastfeed, and/or no longer plans on using DMPA postpartum for contraception, she will be excluded from the study. All other exclusion criteria will again be reviewed to ensure that the subject has not developed any contraindications to DMPA administration

or breastfeeding. If entry criteria are satisfied, the next lowest numbered randomization packet will be opened to determine randomization allocation. All subjects will be informed that pelvic rest is advised for 4-6 weeks.

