### **5.9 Number of subjects and statistical power**

We previously found in a randomized study comparing postplacental and delayed LNG-IUD insertions that only 9% of subjects receiving a postplacental LNG-IUD were breastfeeding at 6 months compared to 41% of subjects receiving a delayed LNG-IUD.(4) We expect breastfeeding continuation rates will be higher in this study since we will be recruiting women who intend to breastfeed. A sample size of 70 per group achieves 80% power ( $\beta=0.20$ ) to detect a difference of 25% between the null hypothesis that the proportion of breastfeeding continuation at 6 months is 0.60 for both groups and the alternative hypothesis that the proportion in group 1 is 0.35 with a significance level of 0.05. With an estimated 10% discontinuation rate prior to randomization and 15% loss-to-follow-up, we plan to enroll 184 subjects

total. Sample size calculations were performed with the two-sided Fisher's Exact test using PASS 2005 (NCSS, Kaysville, UT).

Group 1 (on discharge)	Group 2 (4-6 weeks)	Sample size per group	Total sample size	Including 10% discontinuation/15% LTFU
0.15	0.4	56	112	147
0.25	0.5	64	128	168
0.35	0.6	70	140	184
0.45	0.7	69	138	182

**5.10 Project management:** The study will be coordinated by the Center for Family Planning Research, located in Magee-Womens Hospital at the University of Pittsburgh, which has performed a broad array of family planning research since 1994. The principal investigator and the research coordinator will be responsible for daily monitoring of subject safety. Enrollment, outcomes, and adverse events will be reviewed during biweekly meetings of the investigators and staff. The office has locked storage areas for maintaining subject files. All computers used for database management have firewalls and antivirus software that are updated regularly.

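### The adjusted Cox model leaves out the enrollment Infant Feeding Intentions score: adding it is optional and changes power by about -0.1 to +4 points, under assumed score strength

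*Combined protocol and SAP*

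**What the plan says.** - **Adjusted model (5.8, item 2).** "Cox proportional hazards model will be used to control for age, race, education, marital status, and prior breastfeeding experience". The same item makes the log-rank test the unadjusted comparison.
- **Baseline data (5.4, item d).** The enrollment list includes "Breastfeeding intentions as measured by the Infant Feeding Intentions Scale (29". Item e adds "Psychosocial factors that can affect breastfeeding discontinuation". Neither is given a role in any model, and no reason is stated.
- **Eligibility (5.2 and 5.6).** Inclusion requires "Planning to deliver at Magee-Womens Hospital and to breastfeed". Before discharge a woman is dropped on this condition: "If she has not attempted breastfeeding at least once, does not plan to breastfeed".
- **Order of events (5.6).** Once eligibility is rechecked, "the next lowest numbered randomization packet will be opened to determine randomization allocation". Sections 5.3 and 5.6 also allow enrollment on the postpartum unit, in the same stay as randomization.
- **A second measure of intention (5.6).** "A questionnaire about breastfeeding intentions and whether lactogenesis II has occurred" is to be given before discharge. Its order relative to allocation is not fixed.
- **Review of data (5.10).** "Enrollment, outcomes, and adverse events will be reviewed during biweekly meetings of the investigators and staff".

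**The concern.** A covariate that predicts time to stopping breastfeeding can raise the power of an adjusted Cox test, and this one costs no further data collection. The protocol itself links intention to continuation: section 5.9 expects higher rates here because the women recruited intend to breastfeed. A named baseline scale that is collected but given no analytic use therefore looks like a missed opportunity. At stake is the precision of one analysis, the adjusted hazard ratio for discontinuation. A choice about the score that is left open could also be made later with results in view.

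**Working it through.** **1. The plan's own figure.** Exact power of the two-sided Fisher test for 0.35 vs 0.60 is 0.8095 at 70 per group and 0.7992 at 69, so the stated 70 reproduces. Attrition gives 140 / (0.90 × 0.85) = 183.0, consistent with 184. No covariate enters, so the sizing does not depend on the score.

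**2. The same difference on the Cox scale.** Under proportional hazards the hazard ratio is ln 0.35 / ln 0.60 = 2.06 (log 0.720). With 70 per group fully followed, expected events are 70 × (0.65 + 0.40) = 73.5. Schoenfeld power is Φ(√73.5 / 2 × 0.720 − 1.96) = Φ(1.13) = 0.87. With the 84 events expected in step 3 it is Φ(√84 / 2 × 0.720 − 1.96) = Φ(1.34) = 0.91. This is the starting point if the planned covariates predict nothing.

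**3. Simulation inputs.**
- From the documents: 82 per arm (the budget justification expects 165 randomized), 15% loss, follow-up to day 196, 1:1 allocation, two-sided 5%, continuation 0.35 vs 0.60.
- Assumed: exponential times calibrated to day-182 continuation; random loss; prior breastfeeding experience with log hazard ratio 0.4 per SD and correlation about 0.4 with the score; age and education 0.15 per SD each; score log hazard ratio 0, 0.2, 0.4 or 0.6 per SD beyond the planned covariates.
- 8,000 trials per cell; mean events 84.

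For scale, a hazard ratio of 1.5 per SD (log 0.41) corresponds to about 58% vs 37% breastfeeding at 6 months between the two halves of the score.

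**4. Results at 0.35 vs 0.60.**

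| Score log HR per SD | Planned model | With score | Change (points) | Size-calibrated change |
|---|---|---|---|---|
| 0 | 93.8% | 93.6% | -0.1 | -0.5 |
| 0.2 | 94.4% | 94.8% | 0.3 | 0.4 |
| 0.4 | 95.8% | 97.3% | 1.5 | 1.6 |
| 0.6 | 96.0% | 98.3% | 2.4 | 2.7 |

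Changes come from unrounded power. Their Monte Carlo SE is 0.11 to 0.19 points.

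**5. Validity.** With 0.475 in both arms, type I error over the four score strengths is 5.4, 5.3, 5.8 and 5.7% for the planned model and 5.5, 5.3, 5.7 and 5.9% with the score (SE about 0.25). The two models behave alike.

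**6. Where the gain comes from.** At log hazard ratio 0.4 the mean standard error does not fall (0.235 planned, 0.238 with the score). The median hazard ratio moves from 2.34 to 2.47. This is non-collapsibility: the extended model estimates a slightly more conditional quantity. It does not correct a bias.

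**7. Other assumptions at 0.35 vs 0.60, 82 per arm.**
- Planned covariates uninformative: gains of 0.7, 2.0 and 3.7 at score log hazard ratios 0.2, 0.4 and 0.6.
- About 40% of scores at the ceiling: 0.4, 1.6 and 2.9.
- 10% of scores missing and mean-imputed, at log hazard ratio 0.4: 1.5.
- Planned covariates represented by one index (hazard ratio 1.3 per SD, correlation 0.3 with the score): 0.1, 0.6, 2.5 and 4.0 at score hazard ratios 1.0, 1.25, 1.5 and 1.75, starting from 90.5 to 92.4%.

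The SE of these runs is up to 0.53 points. The upper end is therefore about 4, not a sharp limit.

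**8. Restricted range.** If selecting women who plan to breastfeed halves the score's SD (an assumption), 0.6 per unrestricted SD becomes 0.6 × 0.5 = 0.3 per trial SD. By step 4 the gain then lies between 0.3 and 1.5 points.

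**9. The plan's other rows.** For 0.15 vs 0.40, 0.25 vs 0.50 and 0.45 vs 0.70, under the step 3 assumptions, the change runs from -0.1 to 3.1 points.

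**10. Parameters.** Assuming two race groups, three education levels and binary marital status, the planned model has 1 + 1 + 1 + 2 + 1 + 1 = 7 (treatment, age, race, education, marital status, prior experience), and 8 with the score. Events per parameter go from 84 / 7 = 12.0 to 84 / 8 = 10.5. In the 0.45 vs 0.70 row, with 68.6 events, the extended model has 68.6 / 8 = 8.6.

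**The case against.** The best case against acting is that nothing is broken. The trial was sized on Fisher's exact test, the omitted term does not affect type I error, and the adjusted power is already high. All of that stands and is why the point is optional.

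The size rests on a strength that the documents do not give. The upper end reflects the assumed values: with 70 per arm and no other prognostic covariate, a score hazard ratio of 1.75 per SD gives 6.2 points. The range describes chosen inputs and is not an estimate for this trial.

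The choice of covariate is also open to argument. It is the psychosocial items, not the intentions scale, that section 5.4 describes as able to affect discontinuation. They comprise at least three items with no named scale, so the score is the simpler addition. Entering it as one continuous term is itself an assumption, since the available text does not describe its scoring.

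The most substantive objection concerns timing. Antenatal enrollees may be scored from 24 weeks of gestation. Postpartum enrollees are scored after delivery, perhaps after feeding has been attempted, and in the same stay as randomization. For them, scoring before the packet is opened is implied but not stated. The simulations treat the score as homogeneous. This narrows the remedy but does not defeat it.

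A reader might infer that leaving the score out biases the adjusted comparison. The documents do not support that: allocation is random and prior breastfeeding experience is already in the model. A reader might also infer a routine loss of 6 points or more. Under the main assumptions the change reaches 6.1 only at 0.40 vs 0.60 with a score log hazard ratio of 0.6, and that difference is not one of the plan's scenarios. Nor do the biweekly meetings show that outcomes have been seen by arm: section 5.10 says outcomes are reviewed, not that they are split by group.

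**Conclusion.** The omission is real and unexplained, but the plan is valid as written. Adding the score is an optional, near-free improvement to the adjusted hazard ratio only. At the design difference with 82 per arm, power changes by about -0.1 to +4 points for an assumed score log hazard ratio of 0 to 0.6 per SD. The larger gains arise when the planned covariates carry little information, where power without the score is nearer 91%. The gain may be close to zero, because the entry criteria select women who intend to breastfeed. Confidence is medium: the omission is plain from the text, while the benefit rests on assumed score strength, covariate effects and exponential times.

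**What to change.** Before outcomes by arm are examined, amend 5.8, item 2, by dated amendment. Keep the five covariates and add:

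*The model also includes, as a continuous term, the enrollment Infant Feeding Intentions score, using only scores recorded before the randomization packet is opened. Missing scores, and scores recorded after that point, are replaced by the mean over both arms. The hazard ratio is conditional on all listed covariates.*

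Confirm from the records that women enrolled on the postpartum unit were scored before their packet was opened. Do not substitute the pre-discharge intentions questionnaire. Leave the log-rank test and sample size unchanged.

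If outcomes by arm have already been seen, keep the five-covariate model and report the extended one as a labelled supportive analysis.

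The cost is the amendment, the missing-score rule and one more parameter. If the score is uninformative, about 0.1 points of power are lost (0.5 size-calibrated). The hazard ratio becomes slightly more conditional, and the score mixes antenatal and postpartum measurement times. No new data are needed.
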